#### **7.6.8. Patient related outcome measures**

Postoperative pain, number of analgesic pills taken, and number of days the pills were taken were assessed using questionnaires.

Postoperative questionnaires evaluated the subjects' postoperative pain, interference with daily life, and the patient's perception of swelling using the 100-mm visual analog scale (VAS).

The questionnaire was given to the patients 1 week after surgery. The subjects were also asked to indicate the location of the pain: donor site, recipient site, or elsewhere in the mouth.

## **8. IN VITRO**

### **8.1 Cell culture and HA preparations**

#### **8.1.1 Hyaluronic acid formula**

HA (hyaDENT BG) is a formula containing 1000 kDa monomers of HA cross-linked to butanediol diglycidyl ether (BDDE) complexes and natural HA. (1.6% cross-linked hyaluronic acid and 0.2% natural hyaluronic acid).

#### **8.1.2. Concentration of the hyaluronic acid preparations**

HA will be used at a final concentration of 4 mg/ml in DMEM medium supplemented with 0.3% FBS, as described in the literature. The final concentration of 4 mg/mL was selected to balance biological relevance, experimental feasibility, and clinical translatability. First, previous experiments demonstrated that HA diluted to 4 mg/mL elicited biological responses comparable to those observed with undiluted commercial HA preparations, while allowing improved handling and homogeneous distribution in cell culture conditions [14]. Second, concentrations in the range of 1–5 mg/mL are commonly reported in the literature for in vitro studies evaluating the effects of hyaluronic acid on periodontal and oral cells, particularly under low-serum conditions, supporting the biological validity of this concentration range [36-38]. Third, from a clinical perspective, commercially available HA formulations applied during periodontal surgery are rapidly diluted in situ by blood, gingival crevicular fluid, and saliva. Therefore, the use of a 4 mg/mL concentration in vitro more closely reflects the effective HA concentration at the surgical site after application, rather than the nominal concentration of the undiluted product.

Taken together, these considerations support the use of 4 mg/mL as a biologically active, clinically relevant, and methodologically justified concentration for the present study, with this concentration

range being widely supported by the existing literature on in vitro and translational periodontal models involving hyaluronic acid.

### **8.1.3. Cell culture**

Primary human connective tissue fibroblasts are obtained from each patient undergoing clinical treatment. Tissue samples will be collected from subepithelial palatal connective tissue grafts obtained from systemically and periodontally healthy individuals undergoing periodontal root coverage surgery. Each donor tissue sample will be minced into 1 mm pieces and then pipetted into a 25 cm^3 tissue culture flask and cultured in Dulbecco's modified Eagle's medium (DMEM) supplemented with 10% fetal bovine serum (FBS).

### **8.2. Cell viability assay**

Cell viability can be assessed by CellTiter-Blue viability assay (e.g.) Procedure: After 24 hours of starvation, cells are seeded in triplicate at  $5 \times 10^3$  cells/well in 96-well plates coated with HA at the indicated concentrations (between 0 and 4 mg/mL) prepared in 0.3% FCS/DMEM. 2 hours after seeding, CellTiter-Blue® Reagent (20 µL/well) is added to the cells for 4 hours before recording fluorescence using a luminometer. Experimental values are normalized to the values for untreated cells.

### **8.3. Cell proliferation assay**

The proliferation rates of HA-treated cells are determined using the 5-bromo-2'- deoxyuridine (BrdU) chemiluminescent ELISA (enzyme-linked immunosorbent assay). Procedure: After 24 h of starvation, cells are seeded in triplicate at  $2 \times 10^3$  cells/well in 3% FBS/DMEM in black 96-well microtiter plates coated with HA at a final concentration of 4 mg/ml. Cells were allowed to proliferate for 0, 24, 48, 72 and 96 h before labeling with BrdU for 2 h. The BrdU uptake in the newly synthesized DNA is determined according to the manufacturer's instructions using a luminometer. Experimental values are normalized to the values of untreated control cells at time point 0.

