### **2.1 Study Product Description**

The hyaDENT BG® gel (Fig. 1) is a sterile, resorbable, cross-linked hyaluronic acid preparation specifically designed for dental applications. It is primarily used to support soft tissue healing and regeneration, particularly in mucogingival procedures such as coronally advanced flap (CAF) surgery combined with connective tissue grafting. Its biocompatibility and prolonged residence time at the surgical site enable sustained stimulation of fibroblast migration, angiogenesis, and extracellular matrix synthesis, which are critical for optimal wound healing outcomes.

In periodontal plastic surgery, hyaDENT BG® serves as an adjunctive biomaterial to enhance root coverage predictability and keratinized tissue gain, while reducing patient morbidity associated with donor-site harvesting. Evidence supports its clinical efficacy in improving complete root coverage, reducing postoperative pain and edema, and accelerating the healing process. In addition, its bacteriostatic properties may limit early microbial colonization of the surgical wound.

The product is supplied as a ready-to-use 1.2 ml glass cartridge, containing a transparent, highly viscous gel with the following composition per 1 ml:

- 16 mg cross-linked hyaluronic acid
- 2 mg natural hyaluronic acid
- 6.9 mg sodium chloride
- Water for injection up to 1.0 ml

**Fig 1:** hyaDENT BG®

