#### Surgical technique:

- Local infiltrative anesthesia (2% lidocain with epinephrine at a concentration of 1:100,000)
- Incision design is performed with a microblade (USM-6700) or with a 15c blade
- After flap preparation, a gentle root planing is performed using gracey curettes /mini-five
- Coronal advanced flap is obtained by cutting the superficial muscle fibers using a blade parallel to the external surface of the mucosa.
- Anatomical papillae are de-epithelialized with the scalpel blade and microsurgery scissors.
- The width of the graft was chosen according to the amount of tissue required to cover the exposed root and 3 mm of connective tissue mesial and distal to it.
- Immediately after harvesting, the subepithelial connective tissue graft (SCTG) is placed in a sterile dish
- In the test group, the SCTG is completely immersed (fully soaked) in sterile hyaluronic acid gel
- The graft remains immersed for approximately 1–3 minutes to ensure full surface contact and to prevent dehydration
- Excess hyaluronic acid is allowed to drain passively without compression prior to graft placement

- In the control group, the SCTG is maintained under sterile conditions and hydrated with sterile saline solution for a comparable time interval, without contact with hyaluronic acid

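### The in vitro assays compare HA with untreated cells and no vehicle-matched control, so an effect credited to HA may partly reflect gel vehicle or diluted medium

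*Protocol*

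**What the plan says.** Section 2.1 (Study Product Description) gives the gel's composition per mL: "16 mg cross-linked hyaluronic acid", "2 mg natural hyaluronic acid", "6.9 mg sodium chloride" and "Water for injection up to 1.0 ml". Section 8.1.2 fixes the bench concentration: "HA will be used at a final concentration of 4 mg/ml in DMEM medium supplemented with 0.3% FBS, as described in the literature".

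The assays apply HA as a coating:
- **Section 8.2 (viability):** wells coated with HA at 0 to 4 mg/mL, prepared in medium with 0.3% serum.
- **Section 8.3 (proliferation):** wells coated at a final 4 mg/mL, with cells seeded in medium with 3% serum and followed for up to 96 h.
- **Section 8.4 (migration):** a lower chamber coated at 4 mg/mL in medium with 10% serum, with cells starting in serum-free medium above it.

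The comparator is untreated cells. Section 4.4.2 uses it in H1, H3 and the null hypothesis. Section 8.2 says "Experimental values are normalized to the values for untreated cells" and Section 8.3 says "Experimental values are normalized to the values of untreated control cells at time point 0". No in vitro assay describes a control containing the gel's vehicle or matched for volume.

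The hypotheses in Section 4.4.2 are about the product. Sections 1.1, 6.1 and 9.2 instead describe the aim as finding the effect of HA.

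**The concern.** Adding gel to a culture adds more than HA. It adds salt water without nutrients or serum and, unless corrected, dilutes the medium. Untreated cells get neither. The contrast between treated and untreated wells then combines three things: HA, vehicle, and weaker medium and serum.

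For the question of product against no product, the vehicle is a legitimate part of the exposure. For the question of what HA does, it is not. Dilution of medium and serum is a culture artefact on either reading.

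Proliferation and migration both belong to the primary in vitro hypothesis. Proliferation runs long enough for medium strength to matter. Migration is measured toward a serum-containing chamber, so a lower serum level there would weaken the stimulus itself. The bench work is meant to explain the clinical findings (Section 1.2), so what it can attribute to HA matters.

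**Working it through.** **Inputs**
- Cross-linked HA 16 mg/mL, natural HA 2 mg/mL, sodium chloride 6.9 mg/mL, remainder water (Section 2.1).
- The same HA content as 1.6% and 0.2% (Section 8.1.1).
- Target 4 mg/mL (Section 8.1.2); series 0 to 4 mg/mL (Section 8.2).
- Nominal serum 0.3% (Sections 8.1.2, 8.2), 3% (Section 8.3), 10% (Section 8.4).
- Not stated: coating volume, seeding volume, whether the coating liquid is removed, and whether medium or serum strength is adjusted.

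**1. Reproduce the protocol's own figure.** 16 mg/mL = 1.6% and 2 mg/mL = 0.2%, so total HA = 16 + 2 = 18 mg/mL. Sections 2.1 and 8.1.1 agree.

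**2. Product share of a 4 mg/mL preparation.** Share = target / stock.
- Total HA: 4/18 = 22.2%, a 4.5-fold dilution.
- Cross-linked HA only: 4/16 = 25.0%, a 4-fold dilution.

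**3. Upper end: gel mixed into ready-made medium, no correction, all of it left in the well.** Medium strength = 1 − 0.222 = 77.8% of nominal (75.0% on cross-linked HA only). Serum falls in proportion:
- 0.3% × 0.778 = 0.23%
- 3% × 0.778 = 2.33%
- 10% × 0.778 = 7.8%

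**4. Lower shares: 4 mg/mL is the coating solution and medium is added afterwards.** With r volumes of medium per volume of coating, share = (4/18)/(1 + r). The ratios are assumed:

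| r | Product share of well |
|---|---|
| 0 | 22.2% |
| 0.5 | 14.8% |
| 1 | 11.1% |
| 4 | 4.4% |

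The share approaches 0 if the coating liquid is removed before seeding.

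**5. The Section 8.2 series.** At concentration c, the share of the preparation is c/18. That is 0 at 0 mg/mL, 5.6% at 1 mg/mL (an illustrative intermediate point) and 22.2% at 4 mg/mL. Uncorrected medium strength is then 100%, 94.4% and 77.8%. Any vehicle or dilution effect therefore moves in step with the HA concentration and cannot be separated from a concentration trend.

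**The case against.** The strongest reply is that the confounding is inferred, not shown. A reader might conclude that 22% of every HA well is vehicle and that treated cells get only 78% of the control's medium. The protocol does not support that. Sections 8.2 to 8.4 describe coated surfaces and give no volumes. In Section 8.3 the 3% serum seeding medium differs from the 0.3% serum HA preparation of Section 8.1.2, which suggests that coating and seeding medium may be separate. Section 8.1.2 states a nominal composition and does not say that its strength goes uncorrected. The term final concentration in Sections 8.1.2 and 8.3 favours the higher share but does not settle it. This objection stands: 22% is the top of a range.

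A reader might also infer that the in vitro hypotheses are wrongly framed. They are not. They compare the product with no product, and the salt water belongs to the product. The normalisation sentence in Section 8.3 by itself only sets a time-0 scaling reference; Section 4.4.2 is what fixes the comparator.

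Nor does the clinical control arm, where "the SCTG is maintained under sterile conditions and hydrated with sterile saline solution for a comparable time interval", show that the bench control contradicts the trial. The protocol presents that saline as hydration, not as a vehicle placebo.

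Finally, the viability assay is short: reagent goes in 2 h after seeding and is read 4 h later, which leaves little time for a nutrient effect.

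These points reduce the size and certainty of the problem. They do not supply a control that would exclude it, and the protocol does set out to make statements about HA itself.

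**Conclusion.** The point holds as a design weakness of uncertain size. A 4 mg/mL preparation is about 22% product by volume (25% on cross-linked HA only). The product share of the well is somewhere from near 0 to about 22%, depending on coating and seeding volumes, removal of the coating and any compensation of medium and serum, none of which is stated. With untreated cells as the only comparator, an effect attributed to HA cannot be separated from vehicle or dilution.

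The documents do not give the direction of any bias. Weaker medium would plausibly lower proliferation and so work against HA, but that is an assumption. The product-versus-untreated hypotheses remain coherent, and the clinical primary endpoint is not touched. This is a worthwhile improvement rather than a serious fault.

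**What to change.** In Sections 8.2 to 8.6, add an HA-free control: the same medium and serum, with 6.9 mg/mL sodium chloride solution replacing an equal volume of gel. That is about 22% v/v at 4 mg/mL, scaled as c/18 across the Section 8.2 series. Coat and handle it exactly as the HA preparation.

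Make this control the comparator for statements about HA. Keep the untreated wells for the hypotheses in Section 4.4.2 and for comparison with published data. Leave the GAPDH normalisation in Section 8.5 and the total-protein normalisation in Section 8.6 as they are.

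Also state the coating and seeding volumes, whether the coating liquid is removed, and whether medium and serum strength are matched between wells.

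The cost is one extra control medium and a few more wells, chiefly in the Section 8.2 series.

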#### 8.4. Cell migration assay

Cell migration is tested using Transwell® Polycarbonate Membrane Inserts. Procedure: After 24 hours of starvation,  $5 \times 10^4$  cells are seeded in the upper insert chamber in serum-free DMEM. The lower chamber is coated with HA at a final concentration of 4 mg/mL in 10% FCS/DMEM. Cells are allowed to migrate through the filter for 18 hours at 37°C before fixation and staining with crystal violet. Images of duplicate inserts are acquired using a microscope. Migration is quantified using ImageJ's Fiji distribution.

#### 8.5. RNA analysis by qRT-PCR

For oral fibroblast cells quantitative RT-PCR is used to investigate the expression of COL1A1, COL3A1, TGFB1, TGFB3, PDGFB, FGF2, EGF, IL1A, IL1B, TNF, MMP1, MMP2, MMP3 and MMP8 genes. Procedure: Total RNA from cells treated with HA or growth factor is isolated using the RNeasy Mini Kit. RNA is reverse transcribed and the relative transcripts of the listed genes, normalized to GAPDH, are measured using FastStart Universal SYBR Green Master ROX and primer sequences are shown in the table. Real-time PCR is performed using a 7500 Real-Time PCR system. Data are analyzed using the  $\Delta\Delta C_t$  efficiency method. All samples are run in duplicate.

#### 8.6. Protein analysis by Western Blot

Complete cell extracts of HA-treated oral fibroblasts are prepared by lysis in RIPA buffer. Proteins of interest are visualized using anti-phospho-akt, anti-akt, anti-phospho-erk1/2, anti-erk, anti-phospho-p38, anti-p38 and anti-vinculin antibodies followed by horseradish peroxidase-conjugated secondary antibodies for detection with the SuperSignal™ West Dura Substrate protein immunodetection reagent. The expression of phospho-Akt, phospho-Erk1/2 or phospho-p38 protein relative to the respective total protein control is quantified by densitometry.

### 9. RESULTS

#### 9.1. Clinical Trial

We intend to evaluate the effect of HA, compared to the control group, on clinical parameters:

[figure not shown]
1. Full-mouth plaque score (FMPS)
2. Full-mouth bleeding score (FMBS)
3. Bleeding on probing (BOP)
4. Probing Depth (PD)
5. Clinical attachment level (CAL)

Evaluation times: before treatment, days 4, 8, 15 and every 2 months until 12 months

## 9.2 In-vitro study

[figure not shown]
It is intended to evaluate the effect of HA preparation, compared to control cells, on oral fibroblast cells (obtained from gingival grafts) regarding the:

1. Viability of primary cells. Ability to adhere and assume a fibroblast-specific fusiform morphology (Fig.1);
2. Proliferative and migratory capacity of the cells;
3. Expression of COL3A1 and TGFB3 genes (characterize wound healing without scarring);
4. Expression of genes encoding growth factors and cytokines involved in wound healing;
5. Expression of MMP2 and MMP3 (matrix metalloproteinases) genes
6. Phosphorylation of Akt, Erk1/2 and p38 kinases.

**Fig. 3:** Scanning electron microscope images (SEM) of primary human PDL cells seeded onto dentin discs in control, HA and HA cl samples. PDL cells seeded in cross-linked HA

demonstrated qualitatively more elongated cell morphology when compared to control and HA.

**Fig 4:** Left image: Neutrophils in humans are recruited by IL-8 to injury sites where they release IL-1α and TNF-α and activate fibroblasts and keratinocytes to facilitate wound healing. Right image: Cellular and molecular interactions at the wound site. Fibroblast proliferation and differentiation into myofibroblasts are essential to produce ECM, collagen and α-SMA. Macrophages release mediators that facilitate angiogenesis in order to nourish infiltrated and newly proliferated cells at the wound site (Komi et al).

**Table 1:** General properties and effects of mast cell-derived mediators in the wound healing process (Komi et al.).

Clinic Rev Allerg Immunol

Table 1 General properties and effects of mast cell-derived mediators in wound healing process		
Mediator	General properties and effects in wound healing process	Ref
TGF- $\beta$ 1	
 
• Profibrotic multifunctional growth factor
 
• Stimulates fibroblast proliferation and matrix formation
 
• Some mast cell mediators including protease and chymase through activation of latent TGF-<math>\beta</math>1 contribute in the regulation of extracellular matrix formation
 
	[56]
TGF- $\beta$ 2	
 
• Is involved in:               
 
1. Marked collagen deposition
 
2. Increasing mechanical strength of regenerated tissue
 
3. Accelerating the rate of wound healing
 
 
 
	[56]
Histamine	
 
• Capable of inducing proliferation and collagen synthesis of fibroblasts
 
• Causes the dilatation of arterials and increases permeability of venules
 
	[22] [39]
Chymase	
 
• Possesses mitogenic effect on fibroblasts
 
• Promotes myocardial and skin fibroblast proliferation
 
• Regulates angiotensin (Ang) II generation
 
• Regulates degradation of procollagen protein which participates in tissue remodeling and inflammation
 
	[22, 77] [77]
IL-4	
 
• Increases collagen production
 
• Stimulates accumulation of extracellular matrix macromolecules
 
• Stimulates synthesis of the extracellular matrix proteins including type I and III collagen and fibronectin in fibroblast culture
 
	[22] [78] [22]
mMCP-6	
 
• Stimulates dermal fibroblasts, inducing DNA synthesis in quiescent cells
 
• Increases <math>\alpha</math>-1 collagen production
 
• Stimulates fibroblast and smooth muscle proliferation
 
	[63] [79]
MMP-9	
 
• Facilitates tissue remodeling by degradation of extracellular matrix (ECM)
 
	[80]
mMCP-4	
 
• Human homolog: chymase
 
• Increases fibroblast proliferation
 
• Directly proangiogenic by angiotensin I conversion
 
• Indirectly proangiogenic by modulating ECM, releasing VEGF, and activating progelatinase B
 
• Participates in neutrophil recruitment during the inflammatory phase
 
	[79] [79] [81]
mMCP-5	
 
• Human homolog: elastase
 
• Induces the release of TGF-<math>\beta</math>1
 
	[79]
Trypsin	
 
• Contributes to angiogenesis through directly degrading the ECM components
 
• Releases matrix-bound growth factors owing to its proteolytic activity
 
• Activates latent matrix metalloproteases
 
• Induces endothelial cell proliferation in a dose-dependent manner
 
• Participates in inflammation by leukocyte recruitment
 
• Induces <math>\alpha</math>-SMA expression
 
• Mitogenic for fibroblasts, smooth muscle cells
 
• Possesses chemotactic and mitogenic effects on fibroblasts
 
• Stimulates collagen synthesis
 
• Involved in contraction, and fibroblast differentiation into myofibroblasts
 
	[82] [82] [82] [82] [83] [84] [85] [21] [21] [21]
Carboxypeptidase A	
 
• Increases fibroblast proliferation, and type I collagen production
 
	[53]
bFGF	
 
• Mitogenic factor for fibroblasts, endothelial cells
 
	[86]

